2.2.3 Overall Benefit/Risk Conclusions

CAM2029 has been found to be well-tolerated in clinical trials conducted to date. The overall results from these clinical trials, together with the data from the non-clinical safety, toxicology, and PK studies, support a favorable benefit-risk profile of CAM2029 for further clinical development. Based on the available information, it is considered that the benefits outweigh the risks in the trial patient population.

[figure not shown]
More detailed information about the known and expected benefits and risks and reported AEs after administration of CAM2029 are found in the IB (33).

3 TRIAL OBJECTIVES AND ENDPOINTS

The objectives of this trial and the corresponding endpoints are listed in [Table 1](#).

Table 1: Trial objectives and endpoints

Objectives	Endpoints
Primary Objective	Primary Endpoint

 To evaluate the treatment effect of CAM2029 compared to placebo on liver volume in patients with PLD 	
 Change from baseline to Week 53 in htTLV as determined by MRI volumetry
Key Secondary Objective	Key Secondary Endpoint

 To evaluate the treatment effect of CAM2029 compared to placebo on patient-reported PLD-related symptoms 	
 Change from baseline to Week 53 in the PLD-S measure score
Secondary Objectives	Secondary Endpoints

 To evaluate the treatment effect of CAM2029 on liver volume over time in patients with PLD 	
 Change from baseline in htTLV as determined by MRI volumetry

 To evaluate the treatment effect of CAM2029 on patient-reported PLD-related symptoms over time 	
 Change from baseline in the PLD-S measure score

 To evaluate the treatment effect of CAM2029 over time on kidney volume in patients with presence of kidney cysts 	
 Change from baseline in htTKV as measured by MRI volumetry

 To evaluate treatment effect of CAM2029 over time on total liver cyst volume 	
 Change from baseline in total liver cyst volume determined by MRI volumetry

 To evaluate the treatment effect of CAM2029 over time on renal function in patients with presence of kidney cysts 	
 Change from baseline in eGFR, assessed by the CKD-EPI cystatin C equation using serum concentrations of creatinine and cystatin C

 To evaluate the treatment effect of CAM2029 over time on patient-reported PLD-related impact on functioning and well-being 	
 Change from baseline in the PLD-I measure score

 To evaluate the treatment effect of CAM2029 over time on PLD-related symptoms 	
 Change from baseline in the CGI-S score Change from baseline in the PGI-S score Change from baseline in the PGI-C score

 To evaluate the treatment effect of CAM2029 over time on functioning and well-being 	
 Change from baseline in the SF-36 scores

 To evaluate the treatment effect of CAM2029 over time on PLD-related symptoms 	
 Change from baseline in the PLD-Q score

 To evaluate the safety and tolerability of CAM2029 	
 Incidence of AEs Changes from baseline in laboratory values, vital signs and ECG readings

 To assess the PK of octreotide after administration of CAM2029 	
 Octreotide plasma concentrations over time
Exploratory Objectives	Exploratory Endpoints

AE: adverse event; CGI-S: Clinical Global Impression of Severity; CKD-EPI: Chronic Kidney Disease Epidemiology Collaboration; ECG: electrocardiogram; eGFR: estimated glomerular filtration rate; htTKV: height-adjusted total kidney volume; htTLV: height-adjusted total liver volume; [REDACTED]; IMP: investigational medicinal product; MRI: magnetic resonance imaging; PGI-C: Patient Global Impression of Change; PGI-S: Patient Global Impression of Severity; PK: pharmacokinetics; PLD: polycystic liver disease; PLD-I: Polycystic Liver Disease Impact; PLD-Q: Polycystic Liver Disease Questionnaire; PLD-S: Polycystic Liver Disease Symptoms; [REDACTED]; SF-36: Short Form-36; [REDACTED]

4 INVESTIGATIONAL PLAN

4.1 Overall Trial Design and Plan

This is a Phase 2/3, randomized, placebo-controlled, double-blind, multi-center trial designed to evaluate the efficacy and safety of 2 treatment regimens of CAM2029 versus placebo in patients with PLD. Approximately 69 patients will be included in the trial.

The trial consists of an up to 12-week Screening Period followed by a 52-week (12-month) Double-Blind Treatment Period for which patients will be randomized in a 1:1:1 ratio to 1 of the 3 treatment arms:

- Arm 1: CAM2029 10 mg once weekly
- Arm 2: CAM2029 10 mg once every 2 weeks (weekly alternation with placebo)
- Arm 3: Placebo once weekly

Following completion of the Double-Blind Treatment Period, all patients will continue to a 120-week (30-month), open-label, single-arm, Extension Period with CAM2029 10 mg every 2 weeks, followed by an 8-week Safety Follow-Up Period. The estimated duration of the trial for each patient is approximately 47 months.

A primary endpoint analysis will be performed when the last patient has completed the Double-Blind Treatment Period (Week 53).

An overview of the trial design is shown in [Figure 1](#).

[figure not shown]

Figure 1: Trial design

CL: clinical laboratory sampling; FU: Follow-Up; MRI: magnetic resonance imaging; N: number of patients; R: randomization

4.1.1 Screening Period

Screening assessments will take place within 12 weeks before the Day 1 Visit for patients that have consented to participate in the trial. Screening assessments include, e.g., vital signs, physical examination, ECG, blood and urine sampling, and an MRI volumetric scan. The screening MRI and clinical laboratory sampling will take place within 4 weeks before the Day 1 Visit.

4.1.2 Double-Blind Treatment Period

Eligible patients will receive their first dose of IMP (CAM2029 or placebo) on Day 1. Patients will be treated with IMP as an SC injection every week for a total of 52 weeks. Patients will be

encouraged to perform self- or partner-administration at home, which is allowed after appropriate training (see [Section 6.2.2](#)).

Following Day 1, there will be at least 6 visits during the 52-week Double-Blind Treatment Period (Weeks 5, 13, 21, 25, 39 and 53) for assessment of efficacy, PK, PD and safety. At Week 2, trial personnel will contact the patients by phone to assess any concomitant medication and AEs. Additional visits may be necessary for training of self- or partner-administration of IMP or for IMP administration by trial personnel if self- or partner-administration is not possible. Where applicable, patients will be offered the possibility to complete trial visits at home. In such cases a nurse will come to the patient's home.

Patients who discontinue IMP treatment during the Double-Blind Treatment Period will continue to be followed in the trial and complete all the assessments up to Week 53 (see [Section 6.10.1](#)). A PK sample and an immunogenicity sample should be collected at least 5 weeks after the last dose of IMP.

4.1.3 Open-Label Extension Period

After completion of the 52-week Double-Blind Treatment Period, patients will continue to a 120-week Open-Label Extension Period, in which they will be treated with CAM2029 10 mg administered every 2 weeks. The Extension Period will be offered to patients with an expected positive benefit-risk ratio. The Extension Period will be available only to patients who do not discontinue IMP treatment during the Double-Blind Treatment Period and for whom self- or partner-administration at home is possible. The first dose in the Extension Period will be administered at Week 53, after the last assessments of the Double-Blind Treatment Period have been completed. The last dose will be administered at Week 172. Following the dose at Week 53, there will be at least 8 visits at the clinical site during the Extension Period (Weeks 57, 65, 77, 89, 101, 125, 149 and 173 [End-of-Treatment Visit]) for assessment of efficacy, PK, and safety.

Patients who discontinue IMP treatment during the Extension Period will be asked to complete an End-of-Treatment visit as soon as possible after the last dose of IMP, and a Safety Follow-Up visit at least 5 weeks after last dose of CAM2029 (see [Section 6.10.1](#)). If MRI volumetry has been performed as part of the trial assessments within 1 month prior to the End-of-Treatment Visit, a new MRI is not required.

4.1.4 Safety Follow-Up Period

A Safety Follow-Up Visit will be performed 8 weeks after the Week 173/End-of-Treatment Visit to assess PK and immunogenicity, and to collect information regarding any AEs ongoing at Week 173 and any new SAEs considered related to the IMP.

4.2 Rationale of Overall Trial Design, Endpoints, Trial Population, and Choice of Control Groups and Dose

4.2.1 Overall Trial Design

This is a Phase 2/3, randomized, placebo-controlled, double-blind, multi-center trial designed to evaluate the efficacy and safety of 2 treatment regimens of CAM2029 in patients ≥ 18 years old

with a diagnosis of symptomatic PLD, either in isolation as in ADPLD or in association with ADPKD.

The trial starts with a 52-week (12-month) placebo-controlled, Double-Blind Treatment Period with 2-dosing regimens of CAM2029. Results from trials with SRLs in patients with PLD have shown statistically significant effects on TLV and quality of life after 6 to 12 months of treatment (23, 24, 26, 27). Considering the high bioavailability of CAM2029, together with the inclusion of symptomatic patients with a minimum htTLV of 1800 mL/m (see Section 4.2.3), the probability of reaching significant treatment effects compared to placebo after the 52-week Double-Blind Treatment Period in this trial is considered high (see Section 8.2).

After the 52-week Double-Blind Treatment Period, all patients will be transferred to a 120-week, single-arm, Open-Label Extension Period, in which they will be treated with 10 mg CAM2029 every 2 weeks. Thereby, all patients will receive the active compound and have the opportunity to benefit from the treatment. The Extension Period will also allow monitoring of treatment efficacy and safety over a longer period and for a larger number of patients.

4.2.2 Selection of Endpoints

The primary endpoint in this trial is change in htTLV from baseline to Week 53 assessed by MRI volumetry. Assessment of TLV or htTLV has been used as primary outcome measure in PLD trials since established molecular biomarkers for detection and monitoring of PLD are lacking. Liver volume has been associated with both symptom severity, and quality of life (18).

To assess the PLD-related symptom burden and the impact of disease on functioning and well-being from the patient perspective, two PLD-specific PRO instruments, PLD-S and PLD-I, are currently under development (see Sections 7.3.3.1 and 7.3.3.2). These are included as secondary outcomes to assess treatment effect on patient reported PLD-related symptoms and impact on functioning and well-being, together with evaluation of the effect on liver volume, liver cyst volume and kidney volume (in patients with kidney cysts) over time, health-related quality of life, safety, tolerability and plasma concentrations of octreotide. Treatment effect on renal function in patients with presence of kidney cysts is also included as a secondary endpoint.

[REDACTED]

In addition, the immunogenicity of CAM2029 will be assessed due to the immunogenic potential of octreotide (36).

4.2.3 Trial Population

The trial population is comprised of adult patients (≥ 18 years) who are diagnosed with PLD associated with ADPKD or isolated as in ADPLD. Liver size influences clinical severity in PLD and larger liver volume has been associated with both increasing symptom burden and lower quality of life in patients with PLD (18). The inclusion criterion of htTLV ≥ 1800 mL/m was chosen to provide a patient population that may benefit from the treatment and to show effects on the selected endpoints within the Double-Blind Treatment Period.

To ensure the inclusion of symptomatic patients, presence of at least 1 PLD-related symptom within 2 weeks before screening is required for participation in the trial. The list of PLD-related symptoms was generated from the literature (18) and has been agreed with clinical experts within the field (see Section 5.2). Patients who have been treated with an SRL within 3 months before screening, or who have been non-responsive to previous treatment of PLD with an SRL as per Investigator assessment, are excluded from entering the trial.

Enrolled kidney transplant patients will be monitored according to local clinical practice, including plasma levels of immunosuppressants, at the discretion of the Investigator. Before enrollment of a kidney transplant patient, the Investigator will contact the Medical Monitor who will evaluate each individual case and approve their inclusion in the trial.

[figure not shown]
4.2.4 Dose Rationale

Treatment of patients with PLD with octreotide LAR doses of 40 mg/month has shown promising effects in previous Phase 2 clinical trials with significant impact on TLV (23-25). Due to the higher bioavailability of octreotide for CAM2029 compared with octreotide LAR (Sandostatin LAR), the octreotide exposure is expected to be higher for CAM2029, at the same administered dose of octreotide. In the current Phase 2/3 trial, a weekly dose of 10 mg CAM2029 was therefore selected.

Currently, 30 mg CAM2029 administered every 4 weeks is the highest dose that has been evaluated in Phase 1 clinical trials and this dose was well-tolerated among healthy volunteers (trial HS-11-411). In the current Phase 2/3 trial, 2 dosing regimens of CAM2029 (10 mg once weekly and 10 mg once every 2 weeks) will be evaluated for efficacy and safety in patients with PLD. For 10 mg CAM2029 once weekly, the predicted $C_{max,ss}$ is [REDACTED] ng/mL, which is lower than the observed $C_{max,ss}$ of [REDACTED] ng/mL for 30 mg CAM2029 every 4 weeks (trial HS-11-411) (Figure 2). The predicted overall exposure, calculated as $C_{av,ss} = AUC_{ss}/\text{dose interval}$, for 10 mg CAM2029 once weekly is just slightly higher ([REDACTED] ng/mL) than observed for 30 mg every 4 weeks ([REDACTED] ng/mL). Thus, based on predicted PK data, treatment with 10 mg once weekly is expected to be well-tolerated. Also, a retrospective literature analysis indicated promising results on tolerability when increasing the dose or the dosing frequency of SRLs (37), suggesting that shortening the dose interval of CAM2029 to 10 mg once weekly is not expected to expose the patients to higher risk. Instead, the fluctuation in octreotide plasma concentration will be lower (Figure 2) and a more even octreotide exposure is expected with dosing once weekly compared to monthly dosing of the same total monthly dose of CAM2029.

In addition to an acceptable degree of tolerability, the treatment effect of 10 mg CAM2029 once weekly and 10 mg CAM2029 once every 2 weeks on PLD-related endpoints is expected to be at least that observed in previous trials with Sandostatin LAR. This assumption is based on a higher predicted overall exposure of octreotide for 10 mg CAM2029 once weekly ($C_{av,ss}$ of [REDACTED] ng/mL) and 10 mg CAM2029 once every 2 weeks ($C_{av,ss}$ of [REDACTED] ng/mL) than what is predicted for 40 mg Sandostatin LAR every 4 weeks ($C_{av,ss}$ of [REDACTED] ng/mL).

To evaluate potential differences in efficacy and safety for CAM2029 at different octreotide exposures, a treatment arm with a dosing regimen of 10 mg CAM2029 once every 2 weeks has been included in the trial. As reported above, the predicted exposure (i.e., $C_{av,ss}$) for 10 mg CAM2029 once every 2 weeks is half of that of 10 mg CAM2029 once weekly.

LAR: long-acting release; Obs: observed; OCT: octreotide; Pred: predicted; q1w: once weekly; q2w: once every 2 weeks; q4w: once monthly; ss: steady state

Figure 2: Observed/predicted steady-state octreotide concentration-time profiles after administration of 10 mg CAM2029 q1w and q2w, 30 mg CAM2029 q4w and 40 mg Sandostatin LAR q4w

4.3 Trial Duration

Planned first patient first visit: Q2 2022.

Planned last patient first visit: Q4 2023.

Expected total duration of the trial: Up to 47 months for the individual patient (including screening, Double-Blind Treatment Period, Extension Period and Safety Follow-Up).

4.4 End of Trial Definition

The end of trial for each patient is defined as the last protocol-specified contact with the patient (including follow-up of AEs as described in [Section 4.1.4](#)).

The overall end of trial is defined as the last protocol-specified contact with the last patient ongoing in the trial.

5 SELECTION OF TRIAL POPULATION

5.1 Planned Number of Patients

Approximately 69 patients will be included in this trial.

5.2 Inclusion Criteria

Patients meeting each of the following criteria will be eligible to participate in the clinical trial:

1. Voluntary and valid written informed consent to participate in the trial provided by the patient before any trial related procedures are performed.
2. Male or female patient, ≥ 18 years at screening.
3. Diagnosis of PLD (associated with ADPKD or isolated as in ADPLD) with htTLV ≥ 1800 mL/m at screening.
4. Presence of at least 1 of the following PLD-related symptoms within 2 weeks before screening: bloating, fullness in abdomen, lack of appetite, feeling full quickly after beginning to eat, acid reflux, nausea, rib cage pain or pressure, pain in side, abdominal pain, back pain, shortness of breath after physical exertion, limited in mobility, concern about abdomen getting larger, dissatisfied by the size of abdomen.
5. Not a candidate for, or not willing to undergo, surgical intervention for hepatic cysts during the trial.
6. Female patients of childbearing potential must be willing to use an acceptable method of contraception from screening and during the entire trial (see [Section 7.2.7](#)).
7. Male patients must be willing to use condom as method of contraception from screening and throughout the trial unless they have been sterilized by vasectomy (with an appropriate post-vasectomy documentation of the absence of sperm in the ejaculate).

5.3 Exclusion Criteria

Patients meeting any of the following criteria will not be eligible to participate in the clinical trial:

1. Surgical intervention for PLD within 3 months before screening. *For sclerotherapy patients, at least 6 months before screening.*
2. Treatment with an SSA within 3 months before screening.
3. Non-responsive to previous treatment of PLD with an SSA as per the Investigator's assessment.
4. Symptomatic cholelithiasis within 3 months before screening or previous medical history of cholelithiasis induced by SSAs unless treated with cholecystectomy.
5. Presence of extrahepatic cysts that, in the Investigator's opinion, may prevent the patient from safely participating in the trial.
6. Severe kidney disease, as defined by $\text{eGFR} < 30 \text{ mL/min/1.73 m}^2$.
7. Severe liver disease defined as liver cirrhosis of Child-Pugh class C.
8. Use of oral estrogen contraceptives or supplementation within 3 months before screening.
9. Poorly controlled diabetes (hemoglobin A1c $\geq 10\%$) at screening.
10. Patients with a known history of hypothyroidism, unless they have been on adequate and stable replacement thyroid hormone therapy for at least 3 months before the first dose of the IMP.
11. Uncontrolled hypertension defined by a systolic blood pressure of $> 160 \text{ mmHg}$ and/or diastolic blood pressure of $> 100 \text{ mmHg}$ at screening.

12. History of significant cardiac disease or current diagnosis of cardiac disease indicating significant risk of safety for patients participating in the trial, such as uncontrolled or significant cardiac disease, including any of the following:
 - a. History of myocardial infarction, angina pectoris or coronary artery bypass graft within 6 months before screening.
 - b. Clinically significant cardiac arrhythmias (e.g., ventricular tachycardia), complete left bundle branch block or high-grade atrioventricular block (e.g., bifascicular block, Mobitz type II and third-degree atrioventricular block).
 - c. Long QT syndrome, family history of idiopathic sudden death or congenital long QT syndrome, or any of the following:
 - i. Risk factors for Torsades de Pointes including uncorrected hypokalemia or hypomagnesemia, history of cardiac failure or history of clinically significant/symptomatic bradycardia.
 - ii. Treatment with concomitant medication(s) with a "Known risk of Torsades de Pointes" per www.crediblemeds.org that cannot be discontinued or replaced by safe alternative medication at least 5 half-lives or 7 days (whichever is longer) before the first dose of IMP.
 - iii. Patients with a baseline QTcF >450 msec for males and >470 msec for females at screening.
13. Patients with vascular compromise, including, but not limited to, mesenteric thrombosis, portal hypertension and thrombocytopenia (platelet counts less than $100 \times 10^9/L$).
14. Pregnant, lactating or planning to be pregnant during the trial.
15. Clinically significant laboratory abnormalities, which in the opinion of the Investigator may prevent the patient from safely participating in the trial.
16. History of solid organ transplantation. Exception for kidney transplant patients.
17. Any known allergy, hypersensitivity or intolerance to octreotide or any related drug, or other components of CAM2029, or history of any drug hypersensitivity or intolerance that, in the opinion of the Investigator, would compromise the safety of the patient.
18. Contraindications to, or interference with, MRI assessments, as dictated by local hospital regulations.
19. Previously treated/randomized in the current clinical trial.
20. Participation in any other clinical trial to test an investigational drug or device within the last 30 days before screening or during the trial.
21. Any other contraindicated serious medical condition that, in the Investigator's opinion, may prevent the patient from safely participating in the trial.
22. Any other current or prior medical condition that may interfere with the conduct of the trial or the evaluation of its results in the opinion of the Investigator.
23. Unwilling or unable to comply with the requirements of the protocol or in a situation or condition that, in the opinion of the Investigator, may interfere with participation in the trial.
24. On the staff, affiliated with, or a family member of the personnel directly involved with this trial.

5.4 Lifestyle Considerations

Patients will be advised to avoid fatty or fried foods, and to eat small meals and snacks well distributed over the day, during the first 3 days after the first IMP injection, to avoid loose, pale or fatty stools (26). These symptoms may start 24 hours after first injection of octreotide and last for 1 to 4 days but should subside with subsequent injections.

No other dietary or physical restrictions are required during the trial.

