6.5.2 Randomization and Blinding

The current trial consists of a double-blind treatment period that is followed by an open-label extension period. To minimize bias, patients fulfilling the eligibility criteria will be randomized in a 1:1:1 ratio to 1 of the 3 treatment arms (CAM2029 10 mg once weekly, CAM2029 10 mg every 2 weeks, or placebo) in the double-blind period, using an interactive randomization system (interactive web or voice response system). Before the trial is initiated, the log-in information and directions for the interactive randomization system will be provided to each trial site.

The IMP will be labelled the same for all arms regardless of treatment to ensure blinding. In the treatment arm receiving weekly alternations between CAM2029 and placebo (Arm 2: CAM2029 every 2 weeks, see [Section 4.1](#)), all patients will receive CAM2029 as the initial dose.

The randomized assignment to a treatment arm during the Double-Blind Treatment Period will be revealed to the Sponsor and trial team once the last patient has completed all activities related to Week 53 Visit. At this time point the database is locked and a decision will be made to unblind applicable persons. Patients, Investigators and the trial site team (including site Pharmacy) will remain blinded until the trial is completed, then again, the database is locked and a decision is made to unblind.

In case of emergency, and only if the information is required by the Investigator to ensure a patient's safety in managing a medical condition, the treatment may be unblinded at the trial site by using a code break module. The code break module will be provided by the Sponsor or designee. If possible, the Investigator should contact the Medical Monitor or Sponsor prior to unblinding. The Investigator must also contact the Sponsor after any actions have been taken. Whenever a treatment sequence is prematurely unblinded, the reason, date and time of the unblinding, and the individual who broke the blind must be documented.

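### The dietary advice in Section 5.4 follows the first IMP injection, but for placebo patients the first octreotide injection comes at Week 53, where the advice is not repeated

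*Protocol*

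**What the plan says.** Protocol Section 5.4 (Lifestyle Considerations) advises small, well-spread, low-fat meals "during the first 3 days after the first IMP injection, to avoid loose, pale or fatty stools". It then gives the reason: "These symptoms may start 24 hours after first injection of octreotide and last for 1 to 4 days but should subside with subsequent injections". The section closes by stating that no further dietary restrictions apply in the trial.

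Section 4.1.2 fixes the first IMP injection: "Eligible patients will receive their first dose of IMP (CAM2029 or placebo) on Day 1". For the every-2-weeks arm, which alternates CAM2029 with placebo, Section 6.5.2 states that "all patients will receive CAM2029 as the initial dose". Arm 3 receives placebo weekly throughout the Double-Blind Treatment Period (Section 4.1).

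In the extension, everyone who continues receives CAM2029. Section 4.1.3 says: "The first dose in the Extension Period will be administered at Week 53", after the last double-blind assessments. Entry is restricted: "The Extension Period will be available only to patients who do not discontinue IMP treatment during the Double-Blind Treatment Period", and home administration must be possible. On blinding to the original arm, Section 6.5.2 says: "Patients, Investigators and the trial site team (including site Pharmacy) will remain blinded until the trial is completed".

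**The concern.** The instruction and its reason refer to two different events. The instruction is tied to the first IMP injection, the reason to the first octreotide injection. Where these fall on different days, a site that follows the text gives the precaution at an injection that does not need it and omits it at the one that does.

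What is at stake is tolerability in former placebo patients when they start CAM2029. Neither they nor their site know that the Week 53 dose is a first exposure, because the original arm stays blinded. The schedule of contacts is also thinner than at Day 1. A call or visit at Week 2 follows the Day 1 dose, whereas the next scheduled contact after the Week 53 dose is Week 57. No endpoint or analysis is at stake.

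**Working it through.** The plan states no figure to reproduce on this point. The check compares the two events arm by arm and then counts the patients for whom they differ.

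**Do the events coincide?** (Sections 4.1, 4.1.2, 4.1.3 and 6.5.2; visit days from Table 3)

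| Arm | First IMP injection | First octreotide of the trial | Gap |
|---|---|---|---|
| 1, CAM2029 weekly | Day 1 | Day 1 | 0 days |
| 2, CAM2029 every 2 weeks | Day 1 | Day 1 (CAM2029 is the initial dose) | 0 days |
| 3, placebo weekly | Day 1 | Week 53, Day 365 | 365 − 1 = 364 days (52 weeks) |

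The mismatch is therefore confined to Arm 3. Giving the advice to all patients on Day 1 is right under the blind. What is missing is a repeat at Week 53.

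**Could the wording already cover Week 53?** Section 7.6.1.2 places the first IMP administration on Day 1. Footnote c of Table 3 names the extension explicitly when it means the first IMP doses of that period. So the first IMP injection in Section 5.4 is the Day 1 dose. Section 4.1.3, Section 6.2 and Table 3 with its footnotes do not repeat the advice.

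**How many patients?** Inputs are about 69 patients, 1:1:1 allocation (Section 4.1) and 15% assumed drop-out (Section 8.2).

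- Randomized to placebo: 69/3 = 23, the upper bound.
- Entering the extension = 23 × (1 − proportion not entering). The documents do not give that proportion. Applying the 15% drop-out rate to it is an assumption, so a range is shown:
  - 0%: 23
  - 15%: 23 × 0.85 = 19.55, about 20
  - 30%: 23 × 0.70 = 16.1, about 16

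**Scheduled contact after the Week 53 dose.** The next visit is Week 57, Day 393: 393 − 365 = 28 days later. Symptoms that start about 24 hours after the injection and last 1 to 4 days would be over before then.

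**Effect on the primary analysis.** None. The Week 53 dose is given after the last double-blind assessments.

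**The case against.** The strongest objection is timing. Section 4.3 plans the last patient's first visit for Q4 2023. From the end of that quarter, 12 weeks of screening and 52 weeks of treatment total 64 weeks, or 448 days, which puts the last planned Week 53 dose in late March 2025. The SAP is written against protocol version 8, dated 29 January 2025. On that plan, most or nearly all placebo patients would pass Week 53 before an amendment could take effect. This stands as a limit on benefit: 16 to 23 is the number to whom the gap applies, not the number a change could still help. Actual enrolment dates are not given. It does not make the text right.

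Separate patient instructions may already repeat the advice. They were not available, so the point concerns the protocol text only.

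Investigators are also free to repeat the advice unprompted, since everyone knows the extension dose is CAM2029 and Section 5.4 itself mentions octreotide. That is true, but the text leaves it to chance, and the blind prevents sites from picking out the patients who need it.

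The consequences are already managed. The symptoms are short-lived, anti-diarrheals and pancreatic enzymes are permitted (Section 6.9.1), patients are told to report adverse events arising during home dosing (Section 6.2.2), and gastrointestinal events are of special interest (Section 7.6.1.1). This supports calling the point minor, but these measures respond to symptoms and do not prevent them.

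Two further points stand. The documents show no evidence that the diet works with CAM2029; the source cited for the advice is, by its title, a lanreotide trial. And some placebo patients may have had a somatostatin analog before the trial, since Section 5.3 excludes only use within 3 months before screening or previous non-response. For them Week 53 is the first octreotide of the trial, but not necessarily their first exposure to the class.

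**Conclusion.** The concern holds as a minor tolerability gap in the protocol text. Read literally, Section 5.4 mistimes the precaution by 364 days for placebo patients who enter the extension: at most 23, and about 20 if the 15% drop-out rate carries over to extension entry. These are patients who would start octreotide without a mandated reminder, not patients harmed. They did hear the advice once, on Day 1. The benefit of repeating it cannot be quantified, because neither the frequency of the symptoms nor the effect of the diet is given.

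**What to change.** Keep the Day 1 advice for all patients. Add a clause to Section 5.4 so that the same advice, in identical wording, is given to every patient for the first 3 days after the first Extension Period dose at Week 53. Addressing all patients avoids any signal of the original arm.

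The advice can be delivered at the existing Week 53 visit, with no extra visit, procedure or data collection. The small downside is that patients already on CAM2029 hear advice they do not need. A protocol change still requires a documented amendment agreed by sponsor and investigator (Section 11.1), with ethics committee or authority approval as required (Section 12.1). It would therefore be sensible to check first how many patients have yet to reach Week 53, and to fold the clause into an amendment made for other reasons.
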